Protocol Title: Acceptability of HPV self-sampling tools for cervical cancer prevention in Jamaican women: A theory-based approach to culturally-tailored message design.

Version: 1A

Version Date: April 27, 2018

NCT Number: NCT03613493

1) Protocol Title

Acceptability of HPV self-sampling tools for cervical cancer prevention in Jamaican women: A theory-based approach to culturally-tailored message design.

2) IRB Review History*

N/A

3) Objectives*

The purpose of the proposed study is to increase HPV screening behaviors in Jamaican women by examining the acceptability of HPV DNA self-sampling tools, and determine the most culturally appropriate and effective message design for promoting such a tool in this context.

Specific Aim: Evaluate culturally-tailored HPV DNA self-sampling toolkit.

H1: Women who receive culturally tailored messaging will exhibit improved screening, screening-relevant knowledge, attitudes, and perceived-efficacy.

4) Background*

Low screening coverage is related to health system barriers, as well as women's attitudes and knowledge about cervical cancer screening. In a study conducted by the Ministry of Health and Environment of Jamaica in 2008, lack of uptake was found to be influenced to a significant degree by fears and misconceptions on the part of Jamaican women, including ideas that the human papillomavirus (HPV) test causes damage to the cervix. In addition, other factors impeding women in Jamaica include concerns about privacy, belief that the procedure was embarrassing, ignorance about where to get a pap test, and lack of sufficient information, fear of pain, fear of cervical cancer diagnosis, and lack of sufficient time with their doctors.

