The US Food and Drug Administration has designated HPV screening as a best practice in identifying risk of cervical cancer, over and above pap test screening, because of its high efficacy, affordability, and convenience, since it can be adapted for various settings. The HPV self-sampling tool has been shown to address issues such as privacy, and studies have shown that women feel more comfortable with this option and expressed willingness to recommend the tool to others. This adaptability has become a driving force in advocates support for the tool in hard-to-reach and poor areas. HPV self-sampling has been tested in many contexts, including resource-limited countries, and has been found to be efficacious and cost-effective. With this now fairly well-established in the literature, research questions have now focused on the best strategies for diffusion of the tools. It has been suggested that Community Health Workers (CHWs), coupled with Community-based Participatory Research (CBPR) methods are the ideal vehicle to ensure optimal uptake in community-settings. On the other hand, other studies have proposed that a mailed approach is preferred.

This current proposal aims to determine how culturally appropriate messaging within one context (Jamaica), alongside an innovation (self-sampling HPV test), might increase uptake of screening behaviors.

5) Inclusion and Exclusion Criteria*

Rationale for inclusion/exclusion criteria: This study will involve the collection of data from Jamaican women. Eligible participants will be accepted to the study on a first-come- first-serve basis. A prescreening survey in person or over the phone (see Appendix A), as well as the data from the baseline survey (see Appendix B), which will include a demographic section which will include self-reporting of age etc. (listed below) which will be an additional check for confirming eligibility for the study.

Inclusion criteria: Jamaican women, aged 30 to 65.

Exclusion criteria: women who report having had a hysterectomy, have had a history of cervical cancer, Women who are currently up-to-date on cervical cancer screening (have had a Pap in the last 3 years or have had a Pap smear/HPV co-test within the past 5 years), adults unable to consent, children, pregnant women and prisoners.

6) Number of Subjects*

Total expected: approximately 360 participants, (350 for the intervention; 10 interviews)

7) Study-Wide Recruitment Methods*

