Participants will receive the HPV self-sampler at the time they complete the baseline survey with the Co-I/local study coordinator. The HPV self-sampler kit will include the collection swab and the vial for collecting and storing the specimen, and an instructional sheet that visually depicts the steps for self-sampling. 115 women will receive a culturally-targeted, fear appeal message for the HPV self-sampler kit; 115 women will receive only a fear appeal message, not targeted for the Jamaican populace; and 115 women will receive only the self-sampler tool with no message appeal (plain packaging). (Appendix G & J). The Co-I/local study coordinator will offer the HPV self-sampler accompanied by an instruction sheet on how to use the self-sampler. At this point participants will receive some sensitization on the topic, which will include: 1) health education on the importance of cervical cancer screening using a short intervention/educational script (Appendix H) and 2) motivation to encourage women to have screening using the HPV self-sampler. Women will also be informed of the following: 1) HPV infection usually is not detectable or harmful; 2) nearly everyone who has had sexual intercourse has been exposed to HPV and infection is very common; 3) a positive HPV test result does not indicate the presence of cancer and that not all women who test positive for an HPV infection will not develop advanced cancer. It will also be stressed to women that if they have not seen a doctor recently they will still need to see a provider to address other health issues, which may include a gynecologic exam. They will also be advised that if HPV obtained through self-sampling is positive, they will need follow-up medical care at clinical sites (a list of possible sites will be provided). and to package and return it by mail or to the address provided. A brief survey on intentions will then be administered (Appendix K). Participants will be asked to use the tool at home by following the instructions, The local study coordinator will follow up with participants who do not return the kit within 1 week via SMS messaging. All participants will receive the following message: "Please remember to return your HPV self-sampler kit to X location during the following times: X Y, and Z. Please ignore this message if you have already returned the kit. Thank you."

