All data will be inspected for quality assurance prior to analysis. Prior to performing statistical analysis on quantitative data, the data will be checked, screened and verified. Data checking is critical to ensure the integrity of the database. Range checks will be routinely performed, and random items from the raw data will be checked against the entered data so that mistakes can be identified. the sampling strategy for our study may be described as purposive and snowball sampling. Women will not be not randomly selected as the study was intended to capture a community-based population that meets specific selection criteria. Data will be analyzed from interviews using the constant comparison method (Corbin & Strauss, 2008). For the message design experiment, a paired t-test will be conducted to determine the difference between pre and posttests in screening behavior after exposure to the self-sampling tool; mediation analyses will be conducted to determine if change in screening knowledge, attitudes and perceived-efficacy mediated changes in screening outcomes. Mediation analyses

will be performed using ordinary least squares regression, using techniques recommended for within-subject designs (Judd, Kenny, & McClelland, 2001).

To maintain participant confidentiality, study specific ID codes are used in all study tracking and analyses. Only the Co-I/local study coordinator will have access to the files linking participants with study ID numbers.

13) Provisions to Monitor the Data to Ensure the Safety of Subjects*

All study data collected will be uploaded into the REDCap system. As previously stated, the Co-I and local coordinator have access to this system to enter participant data using an iPad or paper-based methods during interviews and site visits, and in real time during the evaluation phone call.

Furthermore, quality and completeness of data entry will be systematically checked by a data manager at regular intervals for the duration of the study. Only the Co-I has access to the raw data files entered by the Co-I/local study coordinator. De-identified data files that have been cleaned and appropriately grouped and categorized will be made available to study personnel requesting such data.

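### Two of three arms receive a fear appeal, but the stated analysis never compares them with plain packaging and the text names no fear measure, so a backfire could go unnoticed and could not be explained

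*Combined protocol and SAP*

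**What the plan says.** Section 10 (Collection of Self-Samples) describes three equal groups. For the first two it says: "115 women will receive a culturally-targeted, fear appeal message for the HPV self-sampler kit; 115 women will receive only a fear appeal message", the second message not being tailored to Jamaican women. The third group gets the kit in plain packaging with no message. Section 6 plans "350 for the intervention; 10 interviews".

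Section 4 reports that "lack of uptake was found to be influenced to a significant degree by fears and misconceptions on the part of Jamaican women", and its list of obstacles includes "fear of pain, fear of cervical cancer diagnosis".

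The outcomes named in Section 3 (H1) are screening, knowledge, attitudes and perceived efficacy. Section 9 counts the intervention a success if most women return the sample and if knowledge, self-efficacy and response efficacy, or attitudes, improve on baseline. Neither condition is stated by arm. Section 10 adds a short intentions survey (Appendix K), given after the kit and the education and before the woman goes home.

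For analysis, Section 12 gives a paired t-test of screening behaviour before and after exposure, and "mediation analyses will be conducted to determine if change in screening knowledge, attitudes and perceived-efficacy mediated changes in screening outcomes", using techniques for within-subject designs. It states no comparison between message conditions.

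Section 15 attributes emotional discomfort to sensitive questions, and psychological risk to an abnormal test result.

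**The concern.** The protocol identifies fear as a reason women avoid screening and then gives most participants a message built on fear. Such a message could help or hinder, and the plain-packaging arm is what would tell the two apart. The stated analysis does not use that arm. A before/after test and a majority rule over all women can both look favourable while the fear arms do worse than plain packaging.

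Explanation is a second gap. The text names no measure of fear or perceived threat as an outcome or mediator, and none of perceived cultural fit. If targeted and untargeted messages gave different results, the plan as written could not separate tailoring from a difference in how threatening the two messages were. That matters because Section 3 aims to find the most culturally appropriate and effective message design.

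**Working it through.** The documents give no alpha, power, effect size, expected return rate or dropout, so there is no stated power figure to reproduce. Return rates, two-sided 5% and 80% power below are assumptions. Arm sizes are from Section 10.

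**1. Share given a fear appeal.** (115 + 115) / (115 + 115 + 115) = 230/345 = 66.7%. On the planned 350 it is 230/350 = 65.7%; the three groups sum to 5 fewer than 350.

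**2. What each stated criterion can see.**
- *Paired pre/post test (Section 12):* it compares women with themselves. Section 5 excludes women already up to date. If screening behaviour means recent screening, everyone starts near zero, and any return counts as a gain in every arm.
- *Majority return (Section 9):* not stated by arm.
- *Mediation (Section 12):* within-subject change in knowledge, attitudes and efficacy. No term for message condition and no threat measure is named.
- *Posttest (Section 10):* requested upon kit return, so women put off by the message may have no posttest data.

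**3. The majority rule can hide a backfire.** With an assumed 70% return in plain packaging and 45% in both fear arms: (115 × 0.70 + 230 × 0.45) / 345 = (80.5 + 103.5) / 345 = 53.3%. The criterion is met despite a 25-point deficit. An assumed 60% v 46% gives (69 + 105.8) / 345 = 50.7%, also a majority.

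**4. What a direct comparison would see.** Power = Φ[(d − 1.96 × se0) / se1], where se0 uses the pooled proportion and se1 the separate ones. Example, 50% (n = 115) v 40% (n = 230): the pooled proportion is 0.4333, se0 = 0.0566, se1 = 0.0567, and (0.10 − 0.1109) / 0.0567 = −0.19, so power is 42.4%.

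| Plain return (assumed) | Drop in fear arm(s) | Power, 115 v 115 | Power, 230 v 115 |
|---|---|---|---|
| 50% | 10 points | 33.1% | 42.4% |
| 50% | 15 points | 63.5% | 76.3% |
| 50% | 20 points | 87.7% | 95.1% |
| 60% | 10 points | 33.1% | 41.8% |
| 60% | 15 points | 62.6% | 75.1% |
| 60% | 20 points | 86.3% | 94.3% |
| 70% | 10 points | 35.5% | 44.2% |
| 70% | 15 points | 65.3% | 77.3% |
| 70% | 20 points | 87.7% | 95.1% |

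The drop detectable with 80% power is about 16 points for both fear arms v plain and about 18 points for 115 v 115, across plain returns of 50 to 70%. For the 70% v 45% case in step 3, power is 97.4% (115 v 115) and 99.5% (230 v 115).

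**5. Would a fear score be more sensitive?** On a continuous score, 230 v 115 detects 2.802 × √(1/230 + 1/115) = 0.320 SD. For kit return at 50% it is 2.802 × √(0.25 × (1/230 + 1/115)) = 0.160. The SD of a binary outcome at 50% is 0.5, and 0.160/0.5 = 0.320, so the sensitivity is the same. A fear score adds explanation, not power.

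**The case against.** A reader might infer that a failed or backfiring message cannot be recognised at all in this trial. The documents do not support that. There is a no-message arm, kit return is a success criterion, attitudes and efficacy are measured, and intentions are surveyed after exposure. Lower return or intentions in the fear arms than in plain packaging would show a backfire without any fear scale, and a 20-point drop would be detected with about 94–95% power (230 v 115). What is missing is the stated comparison, and then the means to explain its result.

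Nor can one say that the surveys contain no threat items. Appendices B, D, G, J and K are not in the text reviewed, and Section 9 bases the questionnaires on theoretical constructs it does not list. Threat or cultural-fit items may already exist, and the two messages may have been matched for strength. Only their absence from the named outcomes and analyses can be asserted.

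It is also tempting to conclude that the message will add to the barrier. The message text is unseen. Section 10 has all women told that HPV is common and usually harmless and that a positive result does not mean cancer, which bears on fear of diagnosis. The interviews shape the cultural content, although they do not test the finished message.

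Finally, Section 15 is not silent on fear: it mentions fear of how others may react after an abnormal result, and Section 13 provides for monthly review of adverse events and participant feedback. Only distress caused by the message is unlisted.

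All of this stands. It limits the point but leaves the absence of any stated between-arm analysis untouched.

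**Conclusion.** The point holds in this form: 67% of the women receive a fear appeal, Section 4 names fear as a barrier, and the analysis as written never compares fear appeal with plain packaging. A deficit as large as 25 points could coexist with a declared success, given the assumed return rates above. The text names no fear or threat measure, so a deficit that was noticed could not be explained.

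The arms support a comparison that would reliably find a drop of about 16 points or more (both fear arms v plain), but with only about 42–44% power for 10 points. A moderate backfire could be missed even after the fix, and adding a fear score does not change that.

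The conclusion assumes two-sided 5%, plain returns of 50 to 70%, and comparable arms; the text does not say how women are assigned to conditions. It should be corrected before analysis, because the main change is to wording and lets the trial answer its own question.

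**What to change.** **Section 12, the main change.** State two-sided between-arm contrasts on kit return among all enrolled women, with non-return counted as an outcome, and on the post-exposure intentions survey. The contrasts are both fear arms v plain packaging, and targeted v untargeted fear appeal. Report the detectable differences above beside them, so that a null result is not read as no backfire. This costs wording only; the data are already collected.

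**Surveys, only if the appendices lack them.** Add brief perceived-threat items at baseline and in a post-exposure survey. Both are needed because the mediation model works on change, and items asked only after exposure have no baseline. Ask perceived cultural fit in the two message arms only, as a manipulation check; it has no meaning where there is no message. The cost is about a minute of survey time and possible priming, which may be larger in the plain arm because the items bring in fear content just before kit return is measured. Asking after kit return reduces the priming but loses women who do not return the kit.

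**Section 15.** List distress caused by the message beside distress from questions and from abnormal results. This is one sentence.

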After participants return their tests by mail (or do not), results will be analyzed within 6 weeks and sent to the local study coordinator, who will call participants to give the results of their tests. Those who do not return their kit will also be called. All women who test positive for high-risk HPV will receive information on follow-up procedures, which will be available at local health facilities.

In addition to disseminating our findings through journals, conferences, and other standard academic channels, our community partners will oversee the dissemination of research findings within our target communities.

21) Setting

The Co-I/local study investigator will identify and recruit potential subjects at various community venues or NGOs (such as the Jamaica Cancer Society) that they deem appropriate and at which women tend to congregate. These may include, but are not limited to: churches, health clinics, markets health fairs and other events. Parishes that have been identified as low-screening areas will be targeted. Additionally, participants will be asked to refer others to the study by providing the names and phone numbers of up to three additional women.

Interviews will be conducted at a location convenient for the participant or in a private location to be identified (e.g. Jamaica Cancer Society office).

22) Resources Available

- [name] [name] Candidate, Co- Investigator, School of Communication, University of Miami. [name] will be responsible for all aspects of the research implementation, including: data collection and/or management, study coordination, data analysis and/or statistics, participant screening/recruitment, social and/or behavioral assessment, interviews.

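### Staff who give the motivation talk can probably see which package the woman has been offered, so the message comparison is open to uneven encouragement

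*Combined protocol and SAP*

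**What the plan says.** Section 10, under Collection of Self-Samples, sets out three conditions of equal size:

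- First condition, tailored message: "115 women will receive a culturally-targeted, fear appeal message for the HPV self-sampler kit"
- Second condition, general message: "115 women will receive only a fear appeal message, not targeted for the Jamaican populace"
- Third condition, no message: "115 women will receive only the self-sampler tool with no message appeal (plain packaging"

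The same paragraph then describes the visit. "The Co-I/local study coordinator will offer the HPV self-sampler accompanied by an instruction sheet on how to use the self-sampler". Next comes the talk: "At this point participants will receive some sensitization on the topic, which will include: 1) health education on the importance of cervical cancer screening", delivered from the script in Appendix H, and "2) motivation to encourage women to have screening using the HPV self-sampler". Neither part is limited to particular conditions. Women are also given some facts about HPV. After that, "A brief survey on intentions will then be administered (Appendix K". One fixed SMS text is specified for all participants as a reminder to return the kit.

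Section 10 also says, where it discusses tailoring, that the tailored material covers both the package and the instructions. Section 22 says that the Co-I "will be responsible for all aspects of the research implementation", and lists recruitment, data collection and analysis among the duties.

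**The concern.** Packaging is what separates the three conditions. The person who offers the kit also encourages the woman to use it, and the encouragement follows the offer. Unless the package is hidden, that person knows the condition during the step most able to influence whether a kit comes back.

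If the encouragement is warmer or longer with one package than another, the resulting difference in intentions, efficacy or kit return would look like a message effect. Perfect allocation would not prevent this, and a between-condition analysis would not remove it, because the bias enters after allocation and acts on the outcome. It bears directly on H1 in Section 3, which credits improvement to the culturally tailored message.

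**Working it through.** **Order of the visit, from Section 10**

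1. The baseline survey is completed with the Co-I or local study coordinator, and the kit is given at that time.
2. The same staff role offers the kit with an instruction sheet. The package, and possibly the sheet, differs by condition.
3. Education and motivation are given at that point.
4. The intentions survey (Appendix K) follows.

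**What is standardised**

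- Education: a script is named (Appendix H).
- SMS reminder: one fixed text for everyone.
- Motivation: no script is named in the visible text.
- Sight of the condition: no masking, sealed kit or separate staff member is described.

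The documents do not say outright that staff see the condition during the talk. It is a strong inference from steps 2 and 3 and the absence of any concealment.

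**Size**

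The documents give three groups of 115, so 3 × 115 = 345 against an enrolment target of 350 (Sections 6 and 24). They give no return rate, effect size, alpha or power, so there is no planned precision to reproduce. What follows rests on assumed values.

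Standard error of a difference in return between two conditions, with return near 50%:

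SE = sqrt(2 × 0.5 × 0.5 / 115) = sqrt(0.5 / 115) = 0.066, or 6.6 points.

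Assumed shift caused by uneven encouragement:

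- 5 points: 0.05 / 0.066 = 0.76 SE, or 0.05 × 115 = 5.75 women.
- 10 points: 0.10 / 0.066 = 1.52 SE, or 0.10 × 115 = 11.5 women.

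Now suppose the message has no effect, true return is 60% and a two-sided 5% test compares two conditions. With d the shift, SE0 the pooled and SE1 the unpooled standard error, the chance of a significant result in the favoured direction is Φ((d − 1.96 × SE0) / SE1).

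- d = 0.05: SE0 = sqrt(2 × 0.625 × 0.375 / 115) = 0.0638 and SE1 = sqrt((0.65 × 0.35 + 0.60 × 0.40) / 115) = 0.0638, giving about 12%.
- d = 0.10: SE0 = sqrt(2 × 0.65 × 0.35 / 115) = 0.0629 and SE1 = sqrt((0.70 × 0.30 + 0.60 × 0.40) / 115) = 0.0625, giving about 36%.

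Without bias the chance in that direction would be 2.5%.

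**The case against.** A reader might infer that the third condition contradicts itself, since it is described as the tool alone and yet its participants also receive education and motivation. The text does not support that. The parenthesis on plain packaging shows what the restriction refers to, and the second condition is likewise said to receive only a message although those women plainly receive the kit too. What is withheld from the third condition is the message appeal, and it stays withheld.

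A reader might also infer that a talk given to everyone dilutes the message effect. That is possible but not shown. If talk and message add together, the talk raises every condition and the difference is unchanged. Shrinkage needs a ceiling or an overlap in content, and the documents give no return rates or intention scores from which to judge either.

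Further points can fairly be made for the plan:

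- **Unseen appendices.** Appendix H may script the motivation as well as the education. It is not in the text, so this cannot be settled. If it does so identically for all conditions, that part of the point is met, but staff would still see the package.
- **No evidence of uneven delivery.** This stands. The Co-I's range of duties does not show partiality, and the local coordinator may run the visit instead. The point is that a safeguard is absent, not that bias is present.
- **Outcomes.** Kit return is an objective act after the visit, and the intentions survey is not among the success criteria in Section 9. This narrows the part of the point that concerns intentions. It does not protect kit return, which encouragement can still influence.
- **Planned analysis.** Section 12 names a paired pre-post test and within-subject mediation, with no test between conditions. That is a separate gap. The aim and H1 still call for a comparison of messages, and that comparison is what is exposed here.

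**Conclusion.** The point holds as an unguarded route to performance bias. Staff can probably see the condition while motivating the woman, the visible text names no script for the motivation, and no masking is described. A difference between conditions in intentions, efficacy or kit return could therefore partly reflect how hard staff encouraged each group.

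The documents cannot give the size. The range of 0.8 to 1.5 standard errors restates an assumed shift of 5 to 10 points in return, and the 12% and 36% further assume a 60% return rate and no true message effect. The conclusion also assumes that the unseen appendices do not already conceal the condition during the talk.

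The three conditions remain a valid design for the effect of the package message added to standard education. The protocol should say that this is the effect being estimated. This is a cheap improvement, not a fault that invalidates the study.

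**What to change.** In Section 10, fix the order of the visit:

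1. Baseline survey.
2. Education and motivation, including the HPV facts, read from one script that is identical in all conditions. The kit and any tailored instruction sheet stay in an opaque sleeve with no mark of the condition. Staff explain use and return from a generic, untailored sheet.
3. The woman opens the sleeve and views the package.
4. The Appendix K intentions survey at once, before further discussion.

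Describe the third condition as standard education and motivation plus plain packaging. Describe the comparison as the effect of the package message added to that standard talk. If Appendix H already scripts the motivation, say so in Section 10.

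The cost is sleeves, a generic sheet and protocol wording. The steps are already planned, so no extra staff or visits are needed. The downside is small: staff cannot refer to the actual package or tailored sheet during the talk, and the claim is limited to an add-on effect.

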The local study coordinator will transport any samples from the field then batch-shipped to UM Sylvester Comprehensive Cancer Center (SCCC) via DHL. The study coordinator will be in charge of the logistics related to receiving the samples from the field, storing them and shipping them (this corresponds with other projects that have successfully used these methods in the collection of HPV dna samples (see [Lewis-Bell et al. 2013](#)). We will ship the self-sampled specimens to the SCCC for high-risk HPV detection and HPV viral genotyping. Cervical specimens will be labeled with a number that matches the number assigned to the participant during the study intake. The specimens will be

processed and results will be reported back to Co-I within 2 weeks, who will obtain signature from [name]. He will sign and date lab result sheet. Copies of results will be filed and kept in locked cabinet and uploaded to REDCap. Copies of analysis will be given to the study team who will be filed and kept in locked cabinet and uploaded to RedCap.

12) Data Management*

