There are psychological risks associated with receiving an abnormal test result from self-sampling. Participants may interpret an abnormal result as a diagnosis of cancer rather than an infection with HPV. The participant may feel hopeless in response to an abnormal result, believing that there is nothing that can help. As a member of an underserved group she may feel that adequate health services are not available or accessible to her. She may also feel guilty that she has done something wrong or someone has wished ill health upon her. She may feel embarrassed to tell her friends, family, and other ones, fearful of how they may judge her and reflect upon her diagnosis.

If the participant decides that they do not wish to participate in the study after it has started, they will be advised to tell the Co-I or local study coordinator. They will be advised that there is no penalty imposed if they decide to end their participation early and/or refuse to answer any question.

Adverse Experience Reporting: If any participant who chooses to use the HPV self-sampler indicates to the local study coordinator or Co-I that a discomfort is persistent or something else has occurred, the Co-I should contact directly the Principal Investigator and oversight committee of the study. Participants who experience any adverse effect or study-related injury will be navigated to appropriate follow-up care with our community partners and/or The Ministry of Health Jamaica immediately for follow-up care.

16) Potential Benefits to Subjects*

A potential benefit for all participants is the opportunity to be screened. There are no other direct benefits to participants from taking part in the study.

17) Vulnerable Populations*

This research does not involve individuals who are vulnerable to coercion or undue influence or vulnerable populations.

18) Multi-Site Research*

N/A

19) Community-Based Participatory Research*

This project shares some elements of community-engaged research. Firstly, the community will be involved in the conduct of the study as participants, to improve the utilization of local knowledge in the development of an effective intervention or program at a national level. Secondly, we will collaborate with local institutions to plan the research project and for assistance in the recruitment of participants.

20) Sharing of Results with Subjects*

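### Two of the three facts that Section 10 says women will be told are misworded: a stray 'not' turns a reassurance into a warning, and HPV infection is described as usually undetectable

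*Combined protocol and SAP*

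**What the plan says.** In Section 10 (Procedures Involved), the part on collection of self-samples describes what happens when a woman is given the kit. After the health education script and the encouragement to screen comes a further list, introduced by "Women will also be informed of the following". No arm is excepted. The list has three items:

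- **Item 1:** "HPV infection usually is not detectable or harmful".
- **Item 2:** exposure to HPV and infection with it are very common. This item is not in question.
- **Item 3:** two clauses. The first is "a positive HPV test result does not indicate the presence of cancer". The second is "not all women who test positive for an HPV infection will not develop advanced cancer".

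The same paragraph then advises women that a positive self-sample will need medical follow-up, and after that the intentions survey (Appendix K) is given.

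Section 11 (Data and Specimen Banking) states the purpose of the sample: "We will ship the self-sampled specimens to the SCCC for high-risk HPV detection and HPV viral genotyping".

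Section 15 (Risks to Subjects) lists psychological risks of an abnormal result. One is "Participants may interpret an abnormal result as a diagnosis of cancer rather than an infection with HPV". Another is hopelessness.

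**The concern.** The list is an instruction about what participants are to hear. It is not background. If staff follow it as worded, a woman is told that some positive women will go on to advanced cancer, at the point where the plan evidently wants to calm her. She is also told that the infection is usually undetectable while she is being given a test for it.

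Two things are at stake. The first is the accuracy of what women are told on a subject where the plan itself foresees distress. Section 4 (Background) also names misconceptions, and fear of a cancer diagnosis, among the reasons for low uptake. The second is that the statements fall inside the measured interval. Section 9 (Study Endpoints) judges success partly on gains over baseline in knowledge, self-efficacy, response efficacy or attitudes, and Section 12 (Data Management) plans a pre-post analysis.

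**Working it through.** No arithmetic decides this point, and the plan gives no figure to reproduce. The check is logical and textual.

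**Item 3, second clause.** Let P mean that a woman tests positive and A that she develops advanced cancer.

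- As written: NOT (every P is not-A). This is equivalent to: at least one P is A. Some positive women will develop advanced cancer.
- With the second 'not' deleted: NOT (every P is A). This is equivalent to: at least one P is not-A. Some positive women will not develop advanced cancer.

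The two statements can both be true, so the written clause is not shown to be false. What changes is the message: the written form warns and the corrected form reassures. The intent is clear from position, because the clause is joined by 'and' to "a positive HPV test result does not indicate the presence of cancer", which is a correctly worded reassurance.

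**Item 1.** Usually not (detectable or harmful) is equivalent to: usually not detectable and usually not harmful. The second half is not at issue here. The first half, set against the rest of the plan:

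| Place | What it implies about detection |
|---|---|
| Section 10, item 1, read literally | Infection usually cannot be detected |
| Section 10, item 3, first clause | The test can come back positive |
| Section 10, follow-up advice | A self-sample can be positive and then needs follow-up |
| Section 11 | Samples are sent so that high-risk HPV can be detected and typed |

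Item 1 is the one that does not fit. It fits if detectable means noticeable to the woman, but the sentence does not say so.

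**Where the statements fall in time.** The order in Section 10 is baseline survey and kit, education and the three facts, intentions survey, home use and return, posttest. The facts therefore lie between the baseline and both later measurements.

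**Who is covered.** The three arms give 3 × 115 = 345 women; the enrolment target is 350. All receive the same facts.

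**What follows for the comparisons.** Content common to all arms does not by itself create a difference between arms. It is part of what any pre-post change reflects. The direction is unknown: an alarming sentence could lower or raise kit return, and two of the three arms use fear appeals on purpose. The survey items in the appendices are not in the supplied text, so whether either sentence bears on a scored item cannot be checked.

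**The case against.** The strongest reply is that these are drafting slips in a summary of topics and may never be spoken. Where Section 10 intends exact words, as in the text-message reminder, it puts them in quotation marks; the three facts carry none. The educational script is Appendix H, which is not in the supplied text, and the consent form is not there either. Their absence is no fault of the plan, and their wording may be right. This stands as a limit: what women actually hear is not known. It does not clear the protocol text, which introduces the facts as additional to the script and is the only wording available. If Appendix H is right, the protocol should match it.

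A second reply is that the briefing largely corrects itself. The opening clause of item 3 answers the fear that a positive result means cancer, and the follow-up advice makes plain that the kit can give a positive result. This also stands in part. It lessens the harm, but it leaves a woman with statements that do not agree.

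Three stronger readings might be inferred, and the documents do not support them:

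- **A reader might infer that the wording defeats a safeguard in Section 15.** That section lists psychological risks only. It names no safeguard against them and does not refer to this information.
- **A reader might infer that the wording lowers kit return and response efficacy in every arm.** Neither the direction nor the size can be derived.
- **A reader might infer that a few percentage points could decide the return criterion.** Section 9 asks for a majority, but no expected return rate is given, so nothing shows that the result would lie near one half.

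**Conclusion.** The point holds as a wording defect in operative, participant-facing text. In item 3 a stray 'not' reverses the evident reassuring intent of the second clause; the first clause is sound. In item 1 the literal reading conflicts with the purpose of the test in Section 11 and with the follow-up advice in Section 10, though a harmless meaning is likely. Both bear on the misreading of a positive result and the hopelessness listed in Section 15; that link is reasonable, but it is an inference.

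The reach is all 345 to 350 women in the intervention, on the assumption that staff follow the protocol wording. No effect on kit return, knowledge or efficacy scores can be put in figures, and no bias between arms follows from this alone. The correction should be made before the text is used. It is a small change, but it concerns what every woman is told.

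**What to change.** 1. In Section 10, item 3, delete the second 'not', so that the clause says that not all women who test positive will develop advanced cancer.
2. In Section 10, item 1, replace the reference to detectability with wording that does not deny that the offered test can detect HPV. The clinical lead should confirm the intended meaning; if it is that a woman would not notice the infection, the sentence should say that.
3. Check that Appendix H and the consent form agree with the corrected sentences before first use.

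The cost is two reworded sentences and a consistency check of two documents. Design, sample size, analysis and clinical management are unaffected.
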